GI Index Interpretation,

0.1–1.0: Mild gingivitis

1.1–2.0: Moderate gingivitis

2.1–3.0: Severe gingivitis

For measuring plaque accumulation, the Turesky Modified version contains a basis from 0-5, while also distinguishing severity and location. The same six teeth will be used.

The PI scores will indicate as follows,

0: No plaque.

[figure not shown]
1: Separate flecks of plaque at the cervical margin of the tooth.

2: A thin continuous band of plaque at the cervical margin of the tooth.

3: A band of plaque wider than 1 mm covering less than 1/3rd of the crown of the tooth.

4: Plaque covering at least $1/3^{rd}$ but less than $2/3^{rd}$ of the crown of the tooth.

5: Plaque covering $2/3^{rd}$ or more of the crown of the tooth.

Given the environmental advantages of toothpaste tabs, it is worth exploring the effectiveness of tabs following the action of daily brushing within a 2-week trial period.

After measurements are recorded, comparison of the GI & PI results between tabs and conventional toothpaste will be assessed.

a. Endpoints

Primary endpoints

GI and PI scores between the use of dental tablets and conventional toothpaste.

Secondary endpoints

Satisfaction on user-friendliness of both types of toothpastes.

b. Overall study design

A convenience sample of 40 participants will be randomized into two groups containing 20 individuals each. Randomization will be performed by using a randomization table that is generated by the statistician. Selection of participants will concur to a written consent primarily based on voluntary agreement restricted only to a student consensus.

Group A. Colgate Cavity Protection will be selected as the conventional toothpaste for the control group due to its low abrasivity⁸.

Group B. Colgate Anywhere Toothpaste Tablets will be used as the prime cleansing agent for the experimental group.

Subjects will be instructed to use their normal oral hygiene routine throughout a 2-week timeline. New toothbrushes will be used for both groups—Colgate Slim Soft Gliding Tips Toothbrush, Extra Soft, Compact Head.

Group B will be instructed to use Colgate Anywhere toothpaste tablets where one tablet will be used for brushing. Subjects will gently chew on the tablet to dissolve it and will brush for two minutes at least twice a day. Any residual excess from the tablets are to be spit out. Group A will use Colgate Cavity Protection toothpaste and brush at least twice a day for two minutes.

c. Study Procedures and Schedule

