
Subjects will consent to participate. The examiner will then perform an oral examination to provide an evaluation of plaque and gingival **indexes**. Post 2 weeks, a final assessment will be given by the same examiner done in the exact order and technique as the baseline test. The teeth will be reevaluated with new numeric data, where the scores will be added then divided by the total site surfaces. At the end participants will receive a 10-item satisfaction survey.

- d. Alternative procedures \rightarrow N/A
- e. Deception \rightarrow N/A
- f. Investigational New Drug (IND) \rightarrow N/A

7. INCLUSION / EXCLUSION CRITERIA

Inclusion criteria:

- 1. Subjects are 18 years or older;
- 2. Subjects who will comply with study protocol;
- 3. Subjects who can read and understand the consent form;
- 4. Subjects available during the study period;
- 5. Subjects have more than 20 teeth.

Exclusion criteria:

- 1. Subjects who are pregnant and/or nursing;
- 2. Subjects under the age of 18.

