17. STATISTICAL ANALYSIS

We hypothesize that there will be no statistically significant difference in GI and PI scores between the two groups. To test this hypothesis, we will use an independent sample t-test to compare the difference in GI and PI scores between the two groups. If it is determined that GI and/or PI are not normally distributed, we will proceed with testing our hypothesis with the Mann-Whitney U-test. This hypothesis will be tested at an alpha level of 0.05 and will be two-sided. A sample size analysis was conducted and demonstrated that 20 samples per group were necessary to achieve 80% power to test this hypothesis at an alpha level of 0.05.

18. DATA AND SAFETY MONITORING PLAN (DSMP)

N/A

19. LITERATURE REFERENCES

- 1. Gängler, Peter et al. "In vitro effect of fluoride oral hygiene tablets on artificial caries lesion formation and remineralization in human enamel." *BMC oral health* vol. 9 25. 2 Oct. 2009, doi:10.1186/1472-6831-9-25
- 2. Shaikh, Mohammed et al. "Micro computed tomography analysis of abrasivity of toothpaste tablets compared to conventional toothpaste." *American journal of dentistry* vol. 34,5 (2021): 235-239.
- 4. Chasma, Farida, and Gary Cousin. "Keeping Teeth Clean but Not at the Environment's Expense." *Faculty Dental Journal*, vol. 12, no. 1, 2021, pp. 20–22., https://doi.org/10.1308/rcsfdj.2021.5. https://www.researchgate.net/publication/348155830 Keeping teeth clean but not at the environment's expense
- 5. Moslehzadeh, Kaban. "Quigely Hein Index (modified). *Malmo University*. 27 Apr. 2016, https://www.mah.se/CAPP/Methods-and-Indices/Oral-Hygiene-Indices/Quigely-Hein-Index-modified/
- 6. Lippert F. An introduction to toothpaste its purpose, history and ingredients. *Monogr Oral Sci* 2013; 23:1-14.
- 7. 300 million toothpaste tubes go to landfill. *Br Dent J* 2021; 230-390.

- 8. Löe H. The Gingival Index, the Plaque Index and the Retention Index Systems. J Periodontol. 1967 Nov-Dec;38(6):Suppl:610-6. doi: 10.1902/jop.1967.38.6.610. PMID: 5237684.
- https://aap.onlinelibrary.wiley.com/doi/abs/10.1902/jop.1967.38.6.610?sid=nlm%3Apubmed

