- 9. "Amazon.com: Colgate Anywhere Travel Toothpaste Tablets with Fluoride ..." *Amazon*, https://www.amazon.com/Colgate-Anywhere-Toothpaste-Anti-Cavity-Refillable/dp/B08KQMC5MJ.
- 10. "Cavity Protection Toothpaste: Colgate®." *Cavity Protection Toothpaste* | *Colgate*®, https://www.colgate.com/en-us/products/toothpaste/cc-cavity-protection.
- 11. Moslehzadeh, Kaban. "Quigely Hein Index (modified). *Malmo University*. 27 Apr. 2016, https://www.mah.se/CAPP/Methods-and-Indices/Oral-Hygiene-Indices/Quigely-Hein-Index-modified/
- 12. Wilkins, Esther M., et al. *Clinical Practice of the Dental Hygienist*. 12th ed., Wolters Kluwer, 2017, pp. 372, 400.
- 13. *Amazon.com : Colgate Slim Soft Gliding Tips Toothbrush, extra soft ...* (n.d.). Retrieved August 30, 2022, from https://www.amazon.com/Colgate-Gliding-Toothbrush-Extra-Compact/dp/B07NXDWX78

Schedule of Events

	VISIT 1 (Day/Week/Month)	VISIT 2 (Day/Week/Month)
Informed Consent	X	
Baseline Oral Examination (GI & PI)	X	
Distribution of Product	X	
Post 2-Week Oral Examination (GI & PI)		X
Survey Distribution		X
Weight		
Vital Signs		
Oximetry		
Spirometry		

RESULTS

Table 1. Summary of Gender and Age for Subjects Who Completed the Two-Week Clinical Study

	Nun	Age			
Dentifrice	Male	Female	Total	Mean	Range
Sodium Fluoride Toothpaste1	8	12	20	25	18-36
Sodium Fluoride Toothpaste Tablet2	6	14	20	25	19-30

Table 2. Summary of the Baseline Loe-Silness Gingival Index Scores and Quigley-Hein Plaque Index Scores

	Dentifrice	N	Baseline (Mean±SD)		p-value	95% Confidence Interval	
Parameter				Mean Difference		Lower	Upper
Gingivitis	Toothpaste Tablet	20	1.35±0.26	-0.08	0.47	-0.19	0.13
	Conventional Dentifrice	20	1.37±0.24				
Plaque	Toothpaste Tablet	20	2.80±0.58	0.06	0.665	-0.36	0.38
	Conventional Dentifrice	20	2.78±0.46				

Table 3. Summary of the two-week Loe-Silness Gingival Index Scores and Quigley-Hein Plaque Index Scores

Parameter	Dentifrice	N	Two-Week (Mean±SD)		p-value	95% Confidence Interval	
				Mean Difference		Lower	Upper
Gingivitis	Toothpaste Tablet	20	1.33±0.26	-0.06	0.37	-0.167	0.083
	Conventional Dentifrice	20	1.34±0.18				
Plaque	Toothpaste Tablet	20	2.59±0.49	0.08	0.579	-0.25	0.417
	Conventional Dentifrice	20	2.56±0.48				

Table 4. Summary of Within Group Analysis of Loe-Silness Gingival Index and Quigley-Hein Plaque Index Scores

						95% Confidence Interval	
Parameter	Dentifrice	N	Mean Difference	Percent Reduction	p-value	Lower	Upper

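### The interval since last brushing is neither fixed nor recorded before the plaque examinations, which costs the plaque index (PI) comparison precision by an unknown amount

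*Combined protocol and SAP*

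**What the plan says.** Section 6a names as primary endpoints "GI and PI scores between the use of dental tablets and conventional toothpaste". On the plaque scale, Section 6 says: "For measuring plaque accumulation, the Turesky Modified version contains a basis from 0-5". The grades run from no plaque to plaque over two thirds or more of the crown.

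Section 6c describes the baseline visit: "The examiner will then perform an oral examination to provide an evaluation of plaque and gingival" indexes. Of the second visit it says "a final assessment will be given by the same examiner done in the exact order and technique as the baseline test". Examiner, order and technique are therefore held constant.

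Brushing is governed by Section 6b: "Subjects will be instructed to use their normal oral hygiene routine throughout a 2-week timeline", and for the control arm "Group A will use Colgate Cavity Protection toothpaste and brush at least twice a day for two minutes". The tablet arm has the same minimum frequency and duration. The times of day are left to the subject.

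The Schedule of Events lists the two examinations without any pre-visit condition. Section 16 does not list time of last brushing among the data collected. Section 17 plans an unadjusted t-test or Mann-Whitney test, under this hypothesis: "We hypothesize that there will be no statistically significant difference in GI and PI scores between the two groups". It gives no equivalence or non-inferiority margin.

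**The concern.** Brushing removes plaque, and PI scores the plaque that is there when the examiner looks. Under the plan as written, one subject may be scored minutes after brushing and another many hours after. The same subject may also arrive in different states at the two visits. That variation has nothing to do with the product.

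Two things are at stake. The first is the precision of the between-arm PI comparison. Section 12 presents a finding of no difference as the benefit that may lead the public to switch, and Section 17 would reach it through a non-significant superiority test. A noisier endpoint makes non-significance more likely even if the products differ.

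The second is the within-group change in Table 4. At Visit 1 subjects arrive, consent and are examined. At Visit 2 they know that a plaque examination is coming. If they brush closer to the second visit, plaque falls in both arms whatever they used.

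**Working it through.** **Planned sample size.** The 20 per group for 80% power (Section 17) cannot be reproduced forward, because no effect size or SD is given. Solved backwards, the detectable difference is (1.960 + 0.842) × √(2/20) = 0.886 SD by the normal approximation, or 0.909 SD with the noncentral t.

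**Precision of the two-week PI comparison.** Inputs from Table 3: SD 0.49 (tablet), 0.48 (conventional), 20 per arm.

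- Pooled SD = √[(0.49² + 0.48²)/2] = 0.485.
- SE of the difference = √[(0.49² + 0.48²)/20] = 0.153.
- Half-width = 2.024 × 0.1534 = 0.310 (t with 38 df).

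The interval printed in Table 3 (−0.25 to 0.417) has half-width 0.334 and midpoint 0.08, whereas the printed means differ by 2.59 − 2.56 = 0.03. I use the value from the SDs; the proportional effect below is the same either way.

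**Effect of removing timing variation.** Let f be the share of two-week PI variance due to the interval since brushing. This is an assumption, as no value is in the documents. The half-width becomes 0.3105 × √(1 − f):

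- f = 0.05: 0.303
- f = 0.10: 0.295
- f = 0.20: 0.278
- f = 0.30: 0.260

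**Type I error.** Trials with 20 per arm and no true difference were simulated 40,000 times per setting, with extra noise of SD 0, 0.5 or 1 (in units of the underlying SD) added equally to both arms. The t-test rejected in 5.0%, 5.0% and 5.1%. Noise that does not depend on arm leaves the test at its nominal level and costs only power.

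**Can the results tables supply f?** Baseline PI SDs are 0.58 and 0.46 (Table 2). Table 4 gives intervals for the change of −0.453 to 0.005 (tablet) and −0.391 to −0.045 (conventional).

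- SD of change = half-width × √20 / 2.093: 0.229 gives 0.489; 0.173 gives 0.370.
- Correlation between visits, r = (s₀² + s₁² − s_d²)/(2 s₀ s₁): 0.59 (tablet) and 0.69 (conventional), so 1 − r is 0.41 and 0.31.

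These are not values of f. They also include examiner error, real change, the new toothbrush and differing response. Nor are they secure. Paired t-tests from the same intervals give p = 0.055 (t = 0.224/0.1094 = 2.05) and p = 0.016 (t = 0.218/0.0827 = 2.64), whereas Table 4 prints 0.017 and 0.035. If the printed p-values were from paired t-tests, r would be about 0.76 and 0.58, reversing the order of the arms.

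**Within-group falls.** Table 4 reports mean plaque changes of −0.224 and −0.218, differing by 0.006. A common change in pre-visit brushing would produce such a pattern. So would a common effect of the new toothbrush or of taking part. The design cannot separate them.

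**The case against.** The strongest reply is that no effect has been shown. The only time scale the documents give for plaque is 21 days (Section 6, background), with no rate over hours. The share f is assumed, so any gain computed from it merely restates the assumption. This stands: the direction follows from how PI is scored, but the size is unknown and could be small.

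A second reply is that scoring subjects under their usual routine is a defensible pragmatic choice. That partly stands. It does not explain why examiner, order and technique are controlled while the subject's state on arrival is not even recorded.

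Third, subject instructions could sit in the consent form or the recruitment flyer, neither of which was available for this check. Nothing in the protocol points to one.

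A reader might infer more than the documents support:

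- *That the comparison is biased between arms.* Randomisation balances the interval in expectation. Subject masking is not stated and the products look different, so pre-visit brushing could differ by arm, but nothing shows that it did. With 20 per arm, chance imbalance could move the difference either way.
- *That noise in itself favours the tablets.* It helps only because a non-significant result with no margin is taken as support. In an equivalence test with a margin, the same noise would make success harder.
- *That 31–41% of PI variance comes from brushing time.* The calculation above does not isolate it.
- *That pre-visit brushing caused the falls in Table 4.* It cannot be excluded, but it has not been shown.

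**Conclusion.** The omission is real, and it is a design matter rather than a missing detail: following the plan exactly gives a noisier primary endpoint than necessary. The supported harm is lost precision on PI, of a size the documents do not reveal. At an assumed 10–30% share of variance, the half-width would shrink by about 5–16% (1 − √0.9 to 1 − √0.7). Type I error is unaffected and no bias between arms is expected. The loss matters more here than it usually would because of how a non-significant result is to be used. The within-group plaque reductions should not be attributed to either product. The point concerns PI and is not extended to the gingival index. It is worth correcting, but does not by itself invalidate the trial.

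**What to change.** In Section 6c and the Schedule of Events, require one interval since last brushing, chosen by the sponsor and identical for both arms and both visits, with both visits at a similar time of day. Add the time of last brushing to the data collection sheet at each visit.

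Baseline needs care. Consent and the baseline examination share Visit 1, and Section 9 requires written consent before any study activity. Schedule the examination far enough after consent for the interval to be met, or at least record the interval.

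Do not adjust the primary comparison for brushing time at Visit 2. It arises after randomisation, and if it differed by arm, adjustment could itself introduce bias. Report it by arm and use it at most in a sensitivity analysis.

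For the data already collected, state the uncontrolled interval as a limitation, for the within-group changes in particular.

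The cost is one instruction, one field on the data sheet, some rescheduling, possibly a separate consent visit, and slightly less real-world conditions on examination days.

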8. RECRUITMENT AND RETENTION

A flyer will be posted on LLUSD dental hygiene board. Please see attachment.

9. INFORMED CONSENT PROCESS

Informed consent will be obtained in accordance with the Declaration of Helsinki, ICH GCP, US Code of Federal Regulations for Protection of Human Subjects (21 CFR 50.25[a,b], CFR 50.27, and CFR Part 56, Subpart A), the Health Insurance Portability and Accountability Act (HIPAA, if applicable), and local regulations.

Prior to conducting any study-related activities, written informed consent and the Health Insurance Portability and Accountability Act (HIPAA) will be signed and dated by the subject.

The LLUSD East Wing Clinic will be used for the study. The reception desk will be used for student researchers to obtain the consent form from subjects that volunteer and are eligible.

10. SCREENING

On arrival at the reception desk, subjects will be screened for the listed inclusion and exclusion criteria.

11. POTENTIAL RISKS

There is minimal risk going through the clinical examination. However, there may be some jaw pain associated with prolonged mouth opening. Standard of care procedures for clinical oral examination will be followed under the supervision of a licensed dentist (including but not limited to proper PPE, infection control) and the process of assessment and survey will be explained during recruitment.

There is the possibility of a breach of confidentiality, this will be minimized by Subject data will be stored in a locked suite, locked office, and locked cabinet. Data stored electronically is only kept on secure LLU server.

12. POTENTIAL BENEFIT(S)

Potential benefits to subjects and society would be to provide that there is not a clinical or statistical difference in the efficacy of dental tablets versus conventional toothpaste. Providing data that presents no difference in using either tablets or toothpaste may incline the public to switch to an eco-friendlier dentifrice, thus reducing waste. Potential benefits outweigh the risks of this study due to the very low risk involved.

13. SUBJECT WITHDRAWAL OR TERMINATON

Reasons for withdrawal or termination: Subjects will have the freedom to withdraw at any time point of the study.

Handling of subject withdrawals or termination: Records will be kept on subjects that choose to withdraw and the reason why.

Premature termination or suspension of study: N/A

14. **COMPENSATION**

No compensation will be given to participants

15. CONFIDENTIALITY AND PRIVACY

There is the possibility of a breach of confidentiality, this will be minimized by Subject data will be stored in a locked suite, locked office, and locked cabinet. Data stored electronically is only kept on secure LLU server.

16. DATA COLLECTION AND MANAGEMENT RESPONSIBLITIES

Data Collection and Storage

- Data will be collected on the data collection sheet.
- Survey will be completed by the subjects on a hard copy.
- Data will be entered electronically onto an excel spreadsheet.
 - o Paper records will be locked in a secure location
 - Electronic records will be stored on a password-protected or encrypted computer as appropriate based on the sensitivity of data.
- Consent forms will be stored in a locked suite, locked office, and locked cabinet.

• Data will not be transferred outside of LLUH.

Record Retention

1. Records of data/samples generated in the course of this study will be kept for at least 6 years and then destroyed. Prior to destruction, data can be used for other IRB approved research.

17. STATISTICAL ANALYSIS

We hypothesize that there will be no statistically significant difference in GI and PI scores between the two groups. To test this hypothesis, we will use an independent sample t-test to compare the difference in GI and PI scores between the two groups. If it is determined that GI and/or PI are not normally distributed, we will proceed with testing our hypothesis with the Mann-Whitney U-test. This hypothesis will be tested at an alpha level of 0.05 and will be two-sided. A sample size analysis was conducted and demonstrated that 20 samples per group were necessary to achieve 80% power to test this hypothesis at an alpha level of 0.05.

18. DATA AND SAFETY MONITORING PLAN (DSMP)

N/A

19. LITERATURE REFERENCES

- 1. Gängler, Peter et al. "In vitro effect of fluoride oral hygiene tablets on artificial caries lesion formation and remineralization in human enamel." *BMC oral health* vol. 9 25. 2 Oct. 2009, doi:10.1186/1472-6831-9-25
- 2. Shaikh, Mohammed et al. "Micro computed tomography analysis of abrasivity of toothpaste tablets compared to conventional toothpaste." *American journal of dentistry* vol. 34,5 (2021): 235-239.
- 4. Chasma, Farida, and Gary Cousin. "Keeping Teeth Clean but Not at the Environment's Expense." *Faculty Dental Journal*, vol. 12, no. 1, 2021, pp. 20–22., https://doi.org/10.1308/rcsfdj.2021.5. https://www.researchgate.net/publication/348155830 Keeping teeth clean but not at the environment's expense
- 5. Moslehzadeh, Kaban. "Quigely Hein Index (modified). *Malmo University*. 27 Apr. 2016, https://www.mah.se/CAPP/Methods-and-Indices/Oral-Hygiene-Indices/Quigely-Hein-Index-modified/
- 6. Lippert F. An introduction to toothpaste its purpose, history and ingredients. *Monogr Oral Sci* 2013; 23:1-14.
- 7. 300 million toothpaste tubes go to landfill. *Br Dent J* 2021; 230-390.

- 8. Löe H. The Gingival Index, the Plaque Index and the Retention Index Systems. J Periodontol. 1967 Nov-Dec;38(6):Suppl:610-6. doi: 10.1902/jop.1967.38.6.610. PMID: 5237684.
- https://aap.onlinelibrary.wiley.com/doi/abs/10.1902/jop.1967.38.6.610?sid=nlm%3Apubmed
- 9. "Amazon.com: Colgate Anywhere Travel Toothpaste Tablets with Fluoride ..." *Amazon*, https://www.amazon.com/Colgate-Anywhere-Toothpaste-Anti-Cavity-Refillable/dp/B08KQMC5MJ.
- 10. "Cavity Protection Toothpaste: Colgate®." *Cavity Protection Toothpaste* | *Colgate*®, https://www.colgate.com/en-us/products/toothpaste/cc-cavity-protection.
- 11. Moslehzadeh, Kaban. "Quigely Hein Index (modified). *Malmo University*. 27 Apr. 2016, https://www.mah.se/CAPP/Methods-and-Indices/Oral-Hygiene-Indices/Quigely-Hein-Index-modified/
- 12. Wilkins, Esther M., et al. *Clinical Practice of the Dental Hygienist*. 12th ed., Wolters Kluwer, 2017, pp. 372, 400.
- 13. *Amazon.com : Colgate Slim Soft Gliding Tips Toothbrush, extra soft ...* (n.d.). Retrieved August 30, 2022, from https://www.amazon.com/Colgate-Gliding-Toothbrush-Extra-Compact/dp/B07NXDWX78

Schedule of Events

	VISIT 1 (Day/Week/Month)	VISIT 2 (Day/Week/Month)
Informed Consent	X	
Baseline Oral Examination (GI & PI)	X	
Distribution of Product	X	
Post 2-Week Oral Examination (GI & PI)		X
Survey Distribution		X
Weight		
Vital Signs		
Oximetry		
Spirometry		

RESULTS

Table 1. Summary of Gender and Age for Subjects Who Completed the Two-Week Clinical Study

	Nun	Age			
Dentifrice	Male	Female	Total	Mean	Range
Sodium Fluoride Toothpaste1	8	12	20	25	18-36
Sodium Fluoride Toothpaste Tablet2	6	14	20	25	19-30

Table 2. Summary of the Baseline Loe-Silness Gingival Index Scores and Quigley-Hein Plaque Index Scores

	Dentifrice	N	Baseline (Mean±SD)		p-value	95% Confidence Interval	
Parameter				Mean Difference		Lower	Upper
Gingivitis	Toothpaste Tablet	20	1.35±0.26	-0.08	0.47	-0.19	0.13
	Conventional Dentifrice	20	1.37±0.24				
Plaque	Toothpaste Tablet	20	2.80±0.58	0.06	0.665	-0.36	0.38
	Conventional Dentifrice	20	2.78±0.46				

Table 3. Summary of the two-week Loe-Silness Gingival Index Scores and Quigley-Hein Plaque Index Scores

Parameter	Dentifrice	N	Two-Week (Mean±SD)		p-value	95% Confidence Interval	
				Mean Difference		Lower	Upper
Gingivitis	Toothpaste Tablet	20	1.33±0.26	-0.06	0.37	-0.167	0.083
	Conventional Dentifrice	20	1.34±0.18				
Plaque	Toothpaste Tablet	20	2.59±0.49	0.08	0.579	-0.25	0.417
	Conventional Dentifrice	20	2.56±0.48				

Table 4. Summary of Within Group Analysis of Loe-Silness Gingival Index and Quigley-Hein Plaque Index Scores

						95% Confidence Interval	
Parameter	Dentifrice	N	Mean Difference	Percent Reduction	p-value	Lower	Upper
Gingivitis	Toothpaste Tablet	20	-0.026	1.9	0.765	-0.117	0.064
	Conventional Dentifrice	20	-0.011	0.8	0.936	-0.070	0.048
Plaque	Toothpaste Tablet	20	-0.224	8.0	0.017	-0.453	0.005
	Conventional Dentifrice	20	-0.218	7.8	0.035	-0.391	-0.045

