5. OBJECTIVES AND PURPOSE

Due to its travel-friendly size and eco-friendliness, toothpaste tablets have gained popularity among the green people. Green people are those who aim to achieve sustainability. Despite toothpaste tablets' many merits, there is only scarce information on the efficacy, consumer satisfaction, cost, and benefits. Therefore, the purpose of our study is to evaluate the efficacy of toothpaste tablets when compared to conventional toothpaste in removing plaque. We aim to evaluate this by, measuring gingival index (GI) and the plaque index (PI) on subjects that have been either using the tabs or toothpaste.

We hypothesize that there will be no statistically significant difference in GI and PI scores between the two groups. The results of the study will be highly significant as it will serve as a strong piece of evidence to recommend or not to recommend this newly developed product that has the potential to keep our planet safe from non-degradable plastic.

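### Section 17 has only a two-sided difference test and no margin, so a non-significant result cannot support the no-difference benefit that Section 12 names

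*Combined protocol and SAP*

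**What the plan says.** **Hypothesis.** Section 17, like Section 5, states: "We hypothesize that there will be no statistically significant difference in GI and PI scores between the two groups".

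**Test.** Section 17: "To test this hypothesis, we will use an independent sample t-test to compare the difference in GI and PI scores between the two groups". If the scores are not normally distributed, "we will proceed with testing our hypothesis with the Mann-Whitney U-test". Alpha is 0.05, two-sided.

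**Sample size.** Section 17 says that "20 samples per group were necessary to achieve 80% power to test this hypothesis". It gives no effect size, SD or margin.

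**Endpoints.** Section 6a gives the primary endpoints as "GI and PI scores between the use of dental tablets and conventional toothpaste".

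**Intended use.** Section 12 names as a benefit to "provide that there is not a clinical or statistical difference in the efficacy of dental tablets versus conventional toothpaste", and adds: "Providing data that presents no difference in using either tablets or toothpaste may incline the public to switch to an eco-friendlier dentifrice". Section 5 says of the results that "it will serve as a strong piece of evidence to recommend or not to recommend this newly developed product".

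The protocol contains no equivalence or non-inferiority margin, no clinically relevant difference, and no rule for reading a confidence interval. Section 17 does not say what will be concluded if p is above 0.05.

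**The concern.** The t-test and the Mann-Whitney test both take no difference as the null and can only reject it or fail to reject it. Failure to reject says that the data did not reveal a difference. It does not say that the difference is zero or small. Here the conclusion the study hopes for is the null itself, so a small or noisy study is more likely to appear to confirm it. The word clinical in Section 12 also needs a threshold for what matters clinically, and there is none.

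The power statement has the same fault. Power for these tests is the chance of finding a difference of a given size when it exists. It cannot be power for a hypothesis of no difference, and the size it refers to is not stated.

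At stake is the only efficacy conclusion of the study, on both primary indices. A real disadvantage of moderate size could be missed and then reported as grounds for switching to tablets, and no wording in the plan prevents this.

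**Working it through.** **1. The plan's own figure.** The 20 per group cannot be reproduced, because no effect size or SD is given. It can only be solved backwards. For a two-sample t-test with n = 20 per group, the test has 38 degrees of freedom and noncentrality d × √(n/2) = d × √10, where d is the true difference in SD units. At two-sided 0.05:

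| True difference d (SD) | Power | Chance of non-significance |
|---|---|---|
| 0.2 | 0.095 | 0.905 |
| 0.5 | 0.338 | 0.662 |
| 0.636 | 0.50 | 0.50 |
| 0.8 | 0.693 | 0.307 |
| 0.909 | 0.80 | 0.20 |

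The stated 80% is therefore reached only at about 0.91 SD. Below about 0.64 SD, a true difference on a given index is more likely to be missed than found.

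**2. In index points.** The two-week SDs in Table 3 are PI 0.49 and 0.48, and GI 0.26 and 0.18.
- Pooled PI SD = √((0.49² + 0.48²)/2) = 0.485
- Pooled GI SD = √((0.26² + 0.18²)/2) = 0.224

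The 50% point is 0.636 × 0.485 = 0.31 PI points, or 0.636 × 0.224 = 0.14 GI points. The 80% point is 0.909 × 0.485 = 0.44 PI points, or 0.909 × 0.224 = 0.20 GI points.

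**3. What the tabulated data exclude.** The difference is tablet minus toothpaste, and higher is worse. The 95% CI half-width is t(0.975, 38) × SD × √(2/20), with t = 2.024.
- PI: 2.59 − 2.56 = 0.03; half-width 2.024 × 0.485 × 0.3162 = 0.310; CI -0.28 to 0.34
- GI: 1.33 − 1.34 = -0.01; half-width 2.024 × 0.224 × 0.3162 = 0.143; CI -0.15 to 0.13

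Table 3 itself prints a PI difference of 0.08 (CI -0.25 to 0.417) and a GI difference of -0.06 (CI -0.167 to 0.083). Those differences do not match the printed arm means: rounding allows only 0.02 to 0.04 for PI and -0.02 to 0.00 for GI. The tables do not say which test or estimator was used.

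The reading is the same on either set. Table 4 gives two-week reductions of 0.224 and 0.218 for PI, and 0.026 and 0.011 for GI. The upper limits (PI 0.34 or 0.417; GI 0.13 or 0.083) exceed all of these. The reductions are before-after changes without an untreated control, so they serve only as a scale and are not the toothpaste's effect.

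**4. What a margin-based claim would need.** The documents give no margin, so these margins are illustrative. Assumptions: true difference 0, 80% power, 1:1 allocation, no dropout.

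| Claim | n per group, margin 0.5 SD | n per group, margin 0.3 SD | Power at n = 20, margin 0.5 SD |
|---|---|---|---|
| Non-inferiority, one-sided 0.025 (t) | 64 | 176 | 34% |
| Equivalence (TOST), 90% CI | 70 | 191 | 3% |
| Equivalence (TOST), 95% CI | 86 | 235 | 0.2% |

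With 20 per group, 80% power is reached only at a margin of about 0.91 SD for non-inferiority, and about 0.94 SD (90% CI) or 1.05 SD (95% CI) for equivalence.

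**The case against.** Section 17 never says that p above 0.05 will be read as equivalence. The no-difference language sits in a benefits paragraph in conditional wording, Section 5 allows for a recommendation either way, and the results tables carry no equivalence statement. That is fair as to where the wording stands. But Sections 5 and 17 make non-significance the hypothesis, Section 12 states the use intended for it, and nothing in the analysis section limits that use.

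Table 3 already prints between-group CIs. This is true, and it lowers the cost of the fix. What is missing is a planned reading of them, and their centres need reconciling with the arm means.

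The 66% and 0.64 SD figures are per index, while the hypothesis covers both. This stands. If both indices truly differ by 0.5 SD, both tests are non-significant between 0.662² = 44% of the time (independent indices) and 66% (fully correlated), and the 50% point falls to 0.46 SD under independence. These are still high miss rates.

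Section 17 could also mean change scores. Assuming the Table 4 intervals are paired-t CIs, which is uncertain because tablet PI has p = 0.017 with an interval that includes 0, the pooled change SDs are about 0.43 (PI) and 0.16 (GI). The CIs become -0.28 to 0.27 and -0.12 to 0.09. The upper limits still exceed the changes in each arm.

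Finally, results are already tabulated, so this can be called a reporting correction. The remedy is indeed mostly wording, but it governs the main conclusion on both primary endpoints.

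**Conclusion.** The concern holds and must be fixed. As written, the plan contains no analysis that could support the benefit in Section 12, and its power statement does not apply to the hypothesis it names. The 20 per group is not shown to be wrong; it cannot be checked. It gives 80% power at about 0.91 SD and misses a true 0.5 SD difference on one index about two times in three. These figures assume a t-test, equal SDs and complete data. The conversion to index points rests on the printed two-week SDs and is for scale only. The central point needs none of these numbers: a difference test without a margin cannot establish no difference.

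**What to change.** **Section 17, add:** *The between-group difference (tablet minus toothpaste) will be reported with its 95% CI for both GI and PI. If the Mann-Whitney test is used, the Hodges-Lehmann shift and its 95% CI will be reported and labelled as such. A non-significant result will be reported as: no difference detected; differences up to the CI limits are not excluded.*

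**Section 17, power sentence, restate as:** *20 per group gives 80% power to detect a difference of about 0.91 SD; it does not give 80% power to show no difference.* Label the 0.91 SD as back-calculated, or give the actual planning assumption if it is on file.

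**Sections 5 and 12:** align the claims. In Section 12, for example, replace the aim of showing no difference with *estimate the difference, with its 95% CI*.

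**Any non-inferiority or equivalence claim** should be made only against margins for GI and PI that are justified on clinical grounds outside these data. Because results are already tabulated, it must be labelled post hoc.

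**Cost.** Wording in three sections, and one CI per index from data already held, reconciled with the printed arm means. No new subjects are needed for this limited conclusion. The downside is a less favourable claim. A confirmatory claim is not a wording change: it would need a larger study, on the scale shown in step 4 of the working.
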